## **3.2 Exclusion Criteria**

- 3.2.1 Patients may not be receiving any other investigational agents.
- 3.2.2 Patients with known untreated brain metastases.
- 3.2.3 History of allergic reactions attributed to compounds of similar chemical or biologic composition to pioglitzaone.
- 3.2.4 Diagnosis of diabetes mellitus or current therapy with any drugs used to treat diabetes mellitus, including but not limited to insulin, sulfonylureas, metformin, rosiglitazone (Avandia), and pioglitazone (Actos) within 14 days of study Day 1
- 3.2.5 Therapy with rosiglitazone (Avandia) or pioglitazone (Actos) at any time since the diagnosis of thyroid cancer.

- 3.2.6 Uncontrolled intercurrent illness including, but not limited to, ongoing or active infection, congestive heart failure, unstable angina pectoris, or cardiac arrhythmias.
- 3.2.7 Pregnant women are excluded from this study because pioglitazone is a U.S. Food and Drug Administration Pregnancy Category C drug. Because there is an unknown but potential risk for adverse events in nursing infants secondary to treatment of the mother with pioglitazone, breastfeeding should be discontinued if the mother is treated with pioglitazone.
- 3.2.8 No concurrent radiotherapy or chemotherapy may be given to the patient during the administration of the study drug.
- 3.2.9 Patients with uncontrolled malabsorption syndromes.
- 3.2.10 Patients with a history of congestive heart failure of any New York Heart Association class.
- 3.2.11 Any medical or psychiatric illness which, in the opinion of the principal investigator, would compromise the patient's ability to tolerate this treatment regimen.
- 3.2.12 Use of rifampin (strong CYP2C8 inducer) within 14 days of study Day 1.
- 3.2.13 Other current malignancy than the disease under study.
- 3.2.14 Grade 2 or worse edema within 14 days prior to study Day 1, per CTCAE v4.

### **3.3 Inclusion of Women and Minorities**

Both men and women and members of all races and ethnic groups are eligible for this trial.

## **4. TREATMENT PLAN**

### **4.1 Pioglitazone Administration**

This study will be conducted under an exemption of IND (# 113,492) granted by the FDA. Pioglitazone will be obtained from an outpatient pharmacy using a prescription issued by a study investigator.

Drug information is available in the drug package insert (See link in Appendix D).

Treatment will be administered on an outpatient basis. Reported adverse events and potential risks are described in Section 6. Appropriate dose modifications for

pioglitazone are described in Section 5. No investigational or commercial agents or therapies other than those described below may be administered with the intent to treat the patient's malignancy.

Pioglitazone will be administered once daily without regard to meals. The initial dosage will be 30 mg daily, increased to 45 mg after 4 weeks unless side effects require otherwise.

#### **4.2 General Concomitant Medication and Supportive Care Guidelines**

Pioglitazone may decrease the efficacy of oral contraceptive pills. Women taking OCPs also should use barrier contraception.

Levothyroxine should be administered to the same target TSH as would be done if the patient were not enrolled in this clinical trial.

#### **4.3 Duration of Therapy**

Subjects will continue treatment for 28 weeks unless one of the following applies;

- Progressive Disease per RECIST criteria at any time
- Stable Disease per RECIST at 24 weeks
- Best Response per RECIST at 12 weeks and confirmed at 24 weeks
- Intercurrent illness that prevents further administration of treatment
- Unacceptable adverse events
- Patient decides to withdraw from the study
- General or specific changes in the patient's condition render the patient unacceptable for further treatment in the judgment of the investigator.

#### **4.4 Duration of Follow Up**

Patients will be followed for 6 months after removal from study or until death, whichever occurs first. In addition, patients removed from study for unacceptable adverse events will be followed until resolution or stabilization of the adverse event.

#### **4.5 Criteria for Removal from Study**

Patients will be removed from study when any of the criteria listed in Section 4.3 applies. The reason for study removal and the date the patient was removed will be documented in the Case Report Form.

#### **4.6 Continued treatment of responding patients after completion of the study**

Patients who complete the study and are responding without significant adverse effects will be allowed to continue on pioglitazone provided that they are under the care of a study investigator or another appropriately qualified licensed clinician who is willing to use this product "off-label" and can provide them with a prescription.

Patients would be able to use this prescription to obtain the product at any pharmacy. Continued treatment in the “off-label” setting will not be conducted under the auspices of this trial, and continued follow up will not be conducted for study. There are no plans to continue to provide pioglitazone for long-term follow up studies at this time.

#### 4.7 Study Calendar

	Pre-Study	Day 1	Wk 2	Wk 4	Wk 6	Wk 8	Wk 10	Wk 12	Wk 14	Wk 16	Wk 18	Wk 20	Wk 24/ EOT	Wk 28	Post treatment
Pioglitazone a		X													
Informed consent	X														
Demographics	X														
Medical history	X														
Concurrent meds	X														
Physical exam	X							X					X		
Vital signs	X							X					X		
Height	X														
Weight b															
Performance status	X							X					X		
Serum chemistry cd	X	X g				X				X			X		
CBC d	X	X g				X				X			X		
Thyroid blood tests de	X	X g					X						X		
β-hCG df	X														
Adverse event evaluation h	X		X	X				X			X		X		X
Tumor related imaging i	X							X					X	X	
Other correlative studies j	X												X		

a: Dose per protocol; orally administered once daily for 24-28 weeks..

b: Weight obtained at each study site visit and once/week on each subject's same home scale.

c: Pre-Study and Day 1 chemistries: bicarbonate, BUN, chloride, creatinine, glucose, potassium, SGOT[AST], sodium. At weeks 8, 16, 24: glucose, AST.

d: Blood tests can be performed locally.

e: TSH, Free T4, thyroglobulin, thyroglobulin antibodies. All thyroglobulin measurements are to be performed in the same laboratory. Serum thyroglobulin will not be used as a response parameter if endogenous antibodies invalidate the measurement.

f: Pregnancy test in women of childbearing potential only.

g: Within 1 month prior to administration of protocol therapy. Pre-Study assessments if within 1 month will suffice.

h: Adverse events evaluations at weeks 2, 4, 18 and post treatment (within 4 weeks and at 6 months) will be by telephone.

i: Baseline CT or MRI scans must be done within 4 weeks prior to the start of therapy. Baseline CT includes neck, chest and abdomen. Follow-up imaging for disease response is at sites of disease detected at baseline and must include abdomen in cases of elevated AST to evaluate for liver metastases. Week 28 confirmatory CT for patients who need such for RECIST criteria confirmation. Baseline MRI includes: areas with lesions on CT for which there is reasonable diagnostic uncertainty that may be clarified by MRI; and/or brain if clinically indicated.

j: Optional correlative studies at Pre-Study and within 1 day of final dose of pioglitazone. Baseline optional tumor lipid MRI includes areas of measurable disease. Follow-up tumor lipid MRI to be at sites of quantifiable tumor lipid at baseline, and is done at week 24 or end of treatment, whichever comes first.

k: All visits beyond day 1 shall occur at their designated timepoint  $\pm$  5 days.

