## **2. BACKGROUND**

### **2.1 Study Disease**

Follicular carcinoma and follicular variant of papillary carcinoma (together called follicular-patterned thyroid carcinomas) constitute about 15% of thyroid carcinomas. Approximately one-third of follicular carcinomas (1, 2), as well as a subset of follicular variant of papillary carcinomas that has been reported to vary from 0 – 38% (3, 4), contain a chromosomal translocation that fuses the genes encoding PAX8 and PPARgamma, resulting in the production of a PAX8-PPARgamma fusion protein (PPFP).

In general the therapy of thyroid cancer is surgical thyroidectomy followed by radioactive iodine (5). These therapies are effective in the majority of cases, resulting in a 10 year survival of ~85% in follicular carcinoma (6). However, distant metastases occur, primarily in the lung and less commonly in organs such as liver and bone. Metastatic disease is not always responsive to radioiodine – in some cases the tumor concentrates radioiodine but not at sufficient levels to cause a response, and in other cases the metastases do not concentrate radioiodine. There is no accepted chemotherapy or other therapy for these patients, and for these reasons, the median survival of AJCC stage IV follicular carcinoma is only ~4 years (6).

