## **8. MEASUREMENT OF EFFECT**

### **8.1 Antitumor Effect – Solid Tumors**

For the purposes of this study, patients should be re-evaluated for response every 12 ±1 weeks, with a confirmatory CT 4 or more weeks after the 24 week imaging if required by RECIST criteria.

Response and progression will be evaluated in this study using Response Evaluation Criteria in Solid Tumors (RECIST) 1.1.

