### **8.2 Response Criteria (using tumor related imaging CT)**

#### **8.2.1 Evaluation of Target Lesions**

Complete Response (CR): Disappearance of all target lesions

Partial Response (PR): At least a 30% decrease in the sum of the longest diameter (LD) of target lesions, taking as reference the baseline sum LD

Progressive Disease (PD): At least a 20% increase in the sum of the LD of target lesions, taking as reference the

		smallest sum LD recorded since the treatment started or the appearance of one or more new lesions
Stable Disease (SD):		Neither sufficient shrinkage to qualify for PR nor sufficient increase to qualify for PD, taking as reference the smallest sum LD since the treatment started
8.2.2 Evaluation of Non-Target Lesions		
Complete Response (CR):	Disappearance of all non-target lesions and serum tumor marker (thyroglobulin) level $\leq 0.5$ ng/mL	
Incomplete Response/ Stable Disease (SD):	Persistence of one or more non-target lesion(s) and/or serum tumor marker (thyroglobulin) level $> 0.5$ ng/mL	
Progressive Disease (PD):	Appearance of one or more new lesions and/or unequivocal progression of existing non-target lesions	

Although a clear progression of “non-target” lesions only is exceptional, the opinion of the treating physician should prevail in such circumstances, and the progression status should be confirmed at a later time by the review panel (or Principal Investigator).

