### **8.2.3 Evaluation of Best Overall Response**

The best overall response is the best response recorded from the start of the treatment until disease progression/recurrence (taking as reference for progressive disease the smallest measurements recorded since the treatment started). The patient's best response assignment will depend on the achievement of both measurement and confirmation criteria.

Target Lesions	Non-Target Lesions	New Lesions	Overall Response	Best Response for this Category Also Requires:
CR	CR	No	CR	>4 wks. confirmation
CR	Non-CR/Non-PD	No	PR	>4 wks. confirmation
PR	Non-PD	No	PR	
SD	Non-PD	No	SD	documented at least once >4 wks. from baseline

PD	Any	Yes or No	PD	no prior SD, PR or CR
Any	PD*	Yes or No	PD	
Any	Any	Yes	PD	

\* In exceptional circumstances, unequivocal progression in non-target lesions may be accepted as disease progression.

Note: Patients with a global deterioration of health status requiring discontinuation of treatment without objective evidence of disease progression at that time should be reported as "*symptomatic deterioration*". Every effort should be made to document the objective progression even after discontinuation of treatment.

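### Follow-up scans need not cover regions clear at baseline, so the no-new-lesion condition for CR or PR goes unchecked there and the response rate can be biased upward, never downward

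*Combined protocol and SAP*

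**What the plan says.** Footnote i of the study calendar (4.7) sets the coverage of the scans. At entry, "Baseline CT includes neck, chest and abdomen". Afterwards, "Follow-up imaging for disease response is at sites of disease detected at baseline"; the same sentence adds the abdomen when AST is elevated. AST is drawn at weeks 8, 16 and 24 (footnote c), and footnote i gives no threshold for an elevated value.

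Section 8.1 sets the standard: "Response and progression will be evaluated in this study using Response Evaluation Criteria in Solid Tumors (RECIST) 1.1". Under 8.2.1, progression is a 20% increase measured against the "smallest sum LD recorded since the treatment started or the appearance of one or more new lesions". Under 8.2.2, for non-target disease, it is "Appearance of one or more new lesions and/or unequivocal progression of existing non-target lesions". The table in 8.2.3 lists No under new lesions for every row that yields CR, PR or SD, and the text above it says "The best overall response is the best response recorded from the start of the treatment until disease progression/recurrence".

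The primary analysis (9.2) reports the percentage with CR or PR and a 95% binomial confidence interval. Scans are reviewed centrally. Section 9.1 plans 14 evaluable patients and claims 87% power for a 40% rate against 5% or less. No section asks for the remaining baseline regions to be scanned again, or says how new-lesion status is scored for a region that was not imaged.

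**The concern.** The endpoint needs a negative finding, no new lesion, that the imaging schedule does not fully collect. Central review does not help, because it can read only the scans that are taken.

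The gap is concrete in this population. The schema admits locally advanced or recurrent disease as an alternative to metastatic disease (9.1, by contrast, speaks of metastatic disease). A patient with disease only in the neck has no required follow-up chest scan, yet 2.1 says "distant metastases occur, primarily in the lung and less commonly in organs such as liver and bone". A patient with a clear abdomen and normal AST has no required follow-up of the liver. Entry requires progression within the past 14 months (3.1.3), so new lesions are plausible. Thyroglobulin is no safeguard for PR: its 0.5 ng/mL limit enters only the non-target CR definition, and a rise is not part of the definition of progression.

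The error runs one way. A missed lesion can leave a progressing patient classed as SD, PR or CR. Because best response is counted until progression, a lesion missed at week 12 also leaves the window open for a later response. In a single-arm trial whose result is a CR+PR count, nothing offsets this.

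**Working it through.** **Inputs.** From 9.1: n = 14, reference rate 5%, target rate 40%, two-sided 5% level (upper tail 0.025), stated power 87%. From 9.2: exact binomial interval. Not in the documents: q, the share of apparent responders who have a new lesion in a region not re-imaged. I take q from 5% to 30% as an assumption.

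**1. The plan's own figure.** The plan states no decision rule, so I infer one. With X ~ Binomial(14, 0.05):
- P(X ≥ 3) = 0.0301, above 0.025
- P(X ≥ 4) = 0.0042, below 0.025

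The implied rule is at least 4 of 14. With X ~ Binomial(14, 0.40), P(X ≥ 4) = 0.8757, which agrees with the stated 87%.

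**2. One misclassified patient.** 1/14 = 7.1 percentage points. Exact (Clopper-Pearson) 95% limits are the 0.025 quantile of Beta(x, n − x + 1) and the 0.975 quantile of Beta(x + 1, n − x):
- 4/14 = 28.6%, CI 8.4% to 58.1%, excludes 5%
- 3/14 = 21.4%, CI 4.7% to 50.8%, includes 5%

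At this boundary one unseen lesion decides whether the reference rate is excluded.

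**3. A range of misclassification.** Apparent rate = true rate / (1 − q), so true rate = apparent rate × (1 − q).

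| Assumed q | True 5% appears as | P(X ≥ 4 of 14) at that rate | Apparent 40% is truly |
|---|---|---|---|
| 0 | 5.0% | 0.0042 | 40% |
| 5% | 5.3% | 0.0050 | 38% |
| 10% | 5.6% | 0.0061 | 36% |
| 20% | 6.3% | 0.0092 | 32% |
| 30% | 7.1% | 0.0146 | 28% |

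The tail probability stays below 0.025 until q is about 40%. The column that moves materially is the last one: an observed 40% could stand for 28% to 38%.

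**4. How many patients the fix touches.** Apparent responders at a 40% rate: 0.40 × 14 = 5.6, about 6 of 14.

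**The case against.** The best defence is that the gap is narrow. New lesions inside a re-imaged site are seen, and the lung, the main metastatic site, is scanned whenever the chest was involved at baseline. The abdomen is added when AST is raised. A false responder needs two things together: known disease that shrinks enough for CR or PR on central review, and a new lesion confined to a region not imaged. A missed lesion cannot create shrinkage, and 9.1 expects no improvement without treatment. All of this stands, and it limits the claim in four ways.

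- A reader might infer that new-lesion status cannot be verified at all. The documents support this only for regions clear at baseline and not re-imaged. Footnote i does not define a site as lesion, organ or scanned region, so the extent of the gap is itself unclear.
- A reader might infer that the response rate is biased upward as a fact. Without a frequency, only the possibility and the direction are supported.
- A reader might infer a serious loss of type I error control by supposing that a true 5% shows up as 8% or 10%. P(X ≥ 4 of 14) is then 2.1% or 4.4%, but those rates require 1 − 5/8 = 37.5% or 1 − 5/10 = 50% of apparent responders to be misclassified, which is extreme.
- A reader might infer that the plan scores an unscanned region as No. It does not say so. The scoring rule is missing, and 9.2 does have a category for patients who are not assessable.

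A further objection is that requiring a full scan at week 24 or 28 could void a response in a patient who stops treatment before then. That is fair, and it is why the rule has to follow the confirming scan or the end-of-treatment scan. A new lesion found at the confirming scan would count against confirmation under 8.2.3 as it now stands, so scoring it adds no new endpoint rule.

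**Conclusion.** The concern holds in a limited form. Footnote i does not collect what 8.2 requires in regions that were clear at baseline, and no other section fills the gap. Following the plan exactly can count a progressing patient as a responder, and it cannot do the reverse. The frequency is unknown. Each such patient adds 7.1 points to the primary estimate, and at 4 versus 3 of 14 one patient decides whether the interval excludes 5%. The effect is mainly on the point estimate and its interval. Over the assumed 5% to 30% of apparent responders misclassified, the chance of at least 4/14 at a true 5% is 0.5% to 1.5%. This rests on the assumed range for q and on a decision rule inferred from the stated power. It is worth correcting because the error has one direction, touches the primary endpoint and is inexpensive to remove.

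**What to change.** In footnote i and in 8.1, state that:

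- for any patient whose known disease meets CR or PR, the already scheduled scan that confirms the response (week 24 or week 28, or the end-of-treatment scan if the patient stops earlier) repeats all baseline CT fields: neck, chest and abdomen;
- a new lesion found there is scored under 8.2;
- new-lesion status in a baseline region that was not re-imaged is recorded as not assessed, not as No.

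A sentence defining what counts as a site would help, at no cost.

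The price is wider CT coverage at one scheduled scan, with some added radiation and expense, in apparent responders only: about 6 of 14 at a 40% rate. Sample size and stated power do not change.

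Two gaps remain. Progression misread as stable disease in non-responders is not corrected, but it does not add to the responder count. New bone lesions outside the three CT fields would still be missed; those areas are not part of the baseline CT either. Label: cheap improvement.

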### **1.3. Correlative Objectives (Optional)**

Determine (by MRI) if pioglitazone induces lipid accumulation in thyroid carcinomas that contain the PAX8-PPARgamma fusion gene.

Define predictive markers of response or insensitivity to pioglitazone. Unstained tumor tissue slides from archival paraffin blocks, fresh biopsy specimens from measurable metastases, and blood samples (serum and peripheral blood cells) will be collected on enrolled patients who consented for the optional correlative studies. These will be used to identify factors that predict efficacy of pioglitazone. Analyses may include measures of expression of specific RNAs and proteins, and DNA sequence analysis.

Determine if pioglitazone induces a clinically significant level of radioiodine uptake in the residual thyroid carcinoma, and if so, whether there is a therapeutic response to radioiodine. This will be addressed in a separate follow-up protocol available to subjects completing this study.

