### **2.3 Correlative Studies Background**

Serum thyroglobulin levels will be measured. Thyroglobulin is a well established tumor marker in thyroid cancer. Serial serum thyroglobulin measurements are part of the accepted standard of care for thyroid cancer management (5).

Optional for enrolled patients who consent: MRI will be used to assess fat content of the cancer metastases. MRI is an accepted non-invasive method to assess tissue fat content. Our mouse tumor model data indicate that pioglitazone causes a lipogenic response (i.e. the mouse tumors accumulate lipid droplets), which reflects the PPAR $\gamma$ -like action of PPFP. To assess feasibility, we performed thyroid MRIs on two PPFP;Pten $\Delta$  mice that were treated with pioglitazone and two that were not. Thyroid fat content was 13% in the two control diet mice, and 25 to 26% in the pioglitazone-treated mice. This optional MRI consent will allow us to assess whether a similar effect occurs in patients, and will provide another index of a response to pioglitazone.

Optional for enrolled patients who consent: Unstained tumor tissue slides from archival paraffin blocks, and/or fresh biopsy of tumor metastases, and/or peripheral blood (sera and/or DNA) will be collected and stored for potential analyses of tumor markers that may predict response or insensitivity to pioglitazone.

Optional radioiodine scan, and potentially radioiodine therapy, at the end of pioglitazone therapy. In non-PPFP thyroid carcinomas, thiazolidinediones have been shown to induce radioiodine uptake in some patients with otherwise non-iodine avid metastases, although in general the level of uptake has been clinically insignificant (11, 12), with rare exception (13, 14). It seems unlikely that pioglitazone would induce clinically useful radioiodine uptake in PPFP carcinomas, since in the mouse model the thyroid cells differentiate toward adipocytes, not thyrocytes. However, radioiodine uptake in patients should be determined to formally address this question. Patients with clinically significant uptake would be considered for radioiodine therapy, if clinically appropriate. This will be addressed in a separate follow-up protocol available to subjects completing this study.

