The changes in target lesion lipid content at  $24\pm 1$  weeks (or the end of treatment, whichever comes first), compared to pre-study, will be summarized overall and by response. Means and standard deviations or medians and minimum and maximums will be used to summarize the overall patient population at each time. Similarly, statistical descriptions of the response group and the non-response groups will be reported. A paired t-test (or paired Wilcoxon rank test if the data distribution requires it) will be used to compare the changes in target lesion lipid content after treatment to the baseline lipid content in the overall study population with both measurements. In an exploratory analysis, a logistic model will be used with the outcome being response and the independent predictor will be the lipid content change from baseline. The changes in target lesion radioiodine uptake will be summarized overall and by response in a follow-up protocol available to subjects completing this study.

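### The follow-up lipid MRI comes earlier in patients who stop early, so the lipid-by-response analyses in section 9.2 can mistake time on drug for a link with response

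*Combined protocol and SAP*

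**What the plan says.** The tumor lipid MRI is optional. It is done at baseline and once more on treatment. Section 4.7, footnote j, says the follow-up scan "is done at week 24 or end of treatment, whichever comes first"; sections 7.1, 8.3 and 9.2 give the same timing. The footnote also limits which lesions are imaged again: "Follow-up tumor lipid MRI to be at sites of quantifiable tumor lipid at baseline".

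Section 4.3 decides who is still on drug at week 24. Treatment ends for "Progressive Disease per RECIST criteria at any time". It also ends for "Stable Disease per RECIST at 24 weeks" and for "Best Response per RECIST at 12 weeks and confirmed at 24 weeks", so patients with stable disease and week-12 responders both stay on to week 24. Section 8.1 schedules response imaging every 12±1 weeks, which makes week 12 the only planned response scan before week 24.

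Section 9.2 uses the lipid change in three ways. A paired test compares follow-up with baseline in everyone who has both scans. Descriptive summaries are given for responders and non-responders. The third use is labelled exploratory: "a logistic model will be used with the outcome being response and the independent predictor will be the lipid content change from baseline". Responders are patients with CR or PR; all other evaluable patients are non-responders. No time-on-drug term, common scan time or restriction by scan time is planned.

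**The concern.** The outcome being modelled helps to decide when the predictor is measured. Responders are normally scanned at week 24. Non-responders are a mixture: some are scanned at week 24, and some earlier because progression or toxicity ended treatment. Early progression is plausible, since 3.1.3 admits only patients whose disease progressed in the past 14 months. Patients who stop early for unacceptable adverse events also count as evaluable (8.1.1), and those who stop before any response scan fall on the non-responder side.

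If lipid builds up with time on drug, the early scans lower the non-responders' average. More lipid in responders could then appear although lipid has nothing to do with response. That error would favor the study's mechanistic hypothesis. Section 2.3 presents the MRI as a further index of response, so readers are likely to look at this comparison.

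**Working it through.** **The plan's own figures.** The documents give no sample size, power or exposure figure for the lipid analysis. The only power statement concerns the primary endpoint (9.1: 14 evaluable patients, 40% against 5%, two-sided, 87%). It reproduces by exact binomial: with 4 or more responses of 14 required, the upper tail at 5% is 0.0042 and the power at 40% is 0.876. It supplies the group sizes used below: 0.40 × 14 = 5.6, taken as 6 responders and 8 non-responders.

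**Exposure at the scan.** Section 4.1 gives 30 mg daily for 4 weeks, then 45 mg daily.
- Stop at week 12: 28 × 30 + 56 × 45 = 840 + 2,520 = 3,360 mg.
- Week 24: 28 × 30 + 140 × 45 = 840 + 6,300 = 7,140 mg.
- Ratio: 12/24 = 0.50 by weeks; 3,360/7,140 = 0.47 by mg.
- With the ±1-week windows: 11/25 = 0.44 to 13/23 = 0.57 by weeks.
- Stable disease, or progression first found at week 24: ratio 1.00.

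**Exposure of the groups actually compared.** Let q be the share of non-responders who stop at week 12 (not given, so varied), with the rest scanned at week 24. Their mean time on drug is 24 − 12q weeks. The ratio to responders is 1.00 at q = 0, 0.88 at 0.25, 0.75 at 0.5 and 0.50 at 1. Stops before week 12 would lower it further.

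**Effect on the comparison, assuming no true link.** Assumptions:
- All 14 patients are scanned.
- Lipid rises by 12 points by week 24. The only magnitude in the documents is from mice: "Thyroid fat content was 13% in the two control diet mice, and 25 to 26% in the pioglitazone-treated mice", and 25 − 13 = 12.
- SD of the change is 4 or 8 points.
- A two-sample t-test at 5% stands in for the one-predictor logistic model; 20,000 simulated trials per row.

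With a linear rise, a week-12 stopper has gained 6 points instead of 12, so the expected spurious difference is q × 6.

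| Early stops among 8 non-responders | Spurious difference (points) | False positives, SD 4 | False positives, SD 8 |
|---|---|---|---|
| 0 | 0 | 4.9% | 5.0% |
| 2 (q = 0.25) | 1.5 | 6.1% | 5.4% |
| 4 (q = 0.5) | 3.0 | 16.0% | 8.5% |
| 8 (q = 1) | 6.0 | 72.2% | 24.9% |

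If lipid has reached its plateau by week 12, the spurious difference is 0 and the false-positive rate is about 5% in every row. With partial consent (4 responders, 5 non-responders, 2 early stops, linear rise) the rate is 7% at SD 4 and 6% at SD 8.

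**The case against.** The strongest defense is that little rests on this comparison. The MRI objective in 1.3 asks whether the drug induces lipid accumulation. That is a before-and-after question, and the overall paired test answers it. The by-response summaries are descriptive, the logistic model is labelled exploratory, the scan is optional, and no decision is attached to the result. All of this stands. It limits the importance of the point but does not remove the bias, because an exploratory label does not equalize exposure.

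The second defense is that bias needs lipid to keep changing after week 12. The only timing evidence is the mouse study in 2.2, where cells were already full of lipid droplets after 10 weeks of treatment. This is compatible with an early plateau, but it does not establish one in patients.

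Three stronger readings are tempting, and the documents do not support them.
- A reader might infer that progressors as a group are scanned at half the responders' exposure. That holds only for stops at week 12; progression first found at week 24 carries full exposure.
- A reader might infer that the comparison is certainly confounded. Without a lipid time course, the documents support only that it can be.
- A reader might infer that a scan at the end of treatment fails the aim in 1.3 to "Define predictive markers of response or insensitivity to pioglitazone". That paragraph names archival tissue, biopsies and blood, not MRI.

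**Conclusion.** The concern holds as a conditional one. Scan timing is tied to response through the stopping rule, and 9.2 makes no allowance for it. For a week-12 stopper the exposure gap is about twofold. For non-responders as a whole the ratio lies between 0.5 and 1.0 when all stops are at week 12 or later.

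Whether this distorts the lipid-by-response result depends on three things that the documents do not give: the course of tumor lipid after week 12, the share of non-responders who stop early, and the spread of lipid change. Across the moderate cases (two or four early stops of eight), the false-positive rate runs from about 5% to 16%. It is far higher only if every non-responder stops at week 12, and it stays at 5% under a plateau. The primary response endpoint is unaffected. The paired test does pool different exposure lengths, but it makes no responder comparison. The point justifies an inexpensive change to the analysis text, not a redesign.

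**What to change.** Change the wording of 9.2 only. Keep the MRI schedule and the overall paired test.
1. Report weeks on drug at the follow-up MRI for every patient, beside the lipid change.
2. Keep the by-response summary and the logistic model in all patients with both scans, and add the same two analyses restricted to patients scanned at 24±1 weeks.
3. State that any claim that lipid change goes with response will rest on the restricted, equal-exposure comparison.

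No extra scan is needed. When lipid depends only on time on drug, the restricted comparison has its nominal 5% error rate, because everyone in it has the same exposure.

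The cost is precision and scope. With 6 responders and 4 of the 8 non-responders left, the standard error of the difference grows by √(1/6 + 1/4) / √(1/6 + 1/8) = 0.645/0.540, or about 20%. The result describes only patients who stayed on drug to week 24, and leaving out early progressors removes the clearest non-responders. That is why the all-patient version should stay beside it. If every non-responder stops early, the restricted comparison cannot be made, and the report should say so.

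Moving the only follow-up MRI to week 12 would also roughly equalize exposure, but it would shorten the exposure available for the before-and-after objective. That trade is debatable and is not needed here.
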